6. PRIOR AND CONCOMITANT THERAPY

6.1. Prior Therapy

The exclusion criteria (Section 4.2) specify that:

- subjects must not have received any licensed or investigational biologic agent (such as, monoclonal antibodies) within 3 months or 5 half-lives (whichever is longer) prior to the randomization
- subjects must not have received any licensed or investigational nonbiologic agent (such as, those derived from chemical synthesis) within 1 month or 5 half-lives (whichever is longer) prior to the randomization
- subjects must not have received any over-the-counter or prescription medication, including herbal medications, within 28 days prior to the randomization. Use of paracetamol, ibuprofen, and/or vitamins at the recommended dose will be allowed at the investigator's discretion within 28 days prior to the randomization.

6.2. Concomitant Therapy

As the healthy subjects are enrolled in the study, concomitant therapy is not allowed during the study. If medical events (such as, infusion-related reactions, or severe hypersensitivity) occur during the study period, the subjects may receive appropriate medical treatment. The management of infusion-related reactions and severe hypersensitivity is provided in Section 9.7.

All concomitant medications taken during the study will be recorded in the eCRF with indication and dates of administration.

6.3. Potential Interactions Between BGB-DXP593 and Concomitant Medications

The potential for drug-drug interaction between BGB-DXP593 and small-molecule drug products is very low, given that BGB-DXP593 is a monoclonal antibody. Because BGB-DXP593 is expected to be degraded into amino acids and recycled into other proteins, it is unlikely to have an effect on drug metabolizing enzymes or transporters.

7. STUDY PERIODS, VISITS, OR PROCEDURES

Study periods, visits, and procedures are summarized in the following subsections. The timing of all study procedures is provided in the Schedule of Assessments ([Appendix 1](#)).

7.1. Screening Period

Screening evaluation will be performed within 28 days before the single dose of study drug. A subject who agrees to participate in this study will sign the informed consent form (ICF) before undergoing any study-specific procedures. Refer to Section [8.1](#) for instructions regarding screening assessments.

7.1.1. Informed Consent

Voluntary, written informed consent for participation in the study must be obtained before performing any study-specific procedures. ICFs for enrolled subjects and for subjects who are screened but not enrolled will be maintained at the study site. Consent must be obtained using the most current version of the form approved by the IEC/IRB.

For subjects who provide informed consent and subsequently do not meet eligibility criteria or withdraw consent before the single dose of study drug is administered, study site personnel should document the screen failure in the subject's source documents. The documentation should include demographics and medical history, the reason for screen failure, the eligibility criteria reviewed, procedures performed.

7.2. Enrollment

7.2.1. Confirmation of Eligibility

The investigator will assess and confirm the eligibility of each subject. All screening results and relevant medical history must be available before eligibility can be determined. All inclusion criteria must be met and none of the exclusion criteria may apply. No eligibility waivers will be granted.

7.2.2. Subject Numbering

After obtaining informed consent, a unique subject number will be assigned to a potential study participant.

7.3. Check-in (Day -1)

The enrolled subjects will be admitted at least 12 hours prior to the single dose of study drug. On the day of admission, the screening of alcohol/drugs and safety assessment of vital signs will be performed. Smoking will be not allowed during the inpatient stay.

7.4. Randomization

Site personnel will access the IRT system to randomize the treatment assignment. Randomization will occur after the admission on Day -1 and before the dose of study drug on Day 1.

7.5. Treatment (Day 1)

The enrolled subjects will be treated as described in Section 5.2. The study procedures on Day 1 are provided in Appendix 2. Refer to Section 7.7 for additional considerations regarding treatment withdrawal.

7.6. Follow-up Period

The follow-up period starts with the next day following the infusion of study drug and continues until Day 113 of the study. All AEs, including SAEs, will be collected as described in Section 9.6.

7.6.1. Check-out (Day 8)

The subjects will be discharged 7 days after the single dose of study drug. Before the discharge, the procedures and assessments specified in Appendix 1 should be completed.

7.6.2. End-of-Study Visit

Subjects who permanently discontinue from the study will be asked to return to the study center for the End-of-Study (EOS) Visit, which is required to be conducted within 7 days after the premature study discontinuation. The Day 113 Visit is the EOS Visit for subjects who complete all the previously planned study visits.

If a subject refuses to return for the EOS Visit or is unable to do so, every effort should be made to contact the subject by telephone to determine their health status.

7.6.3. Safety Follow-up Visit for Premature Study Discontinuation

If a subject discontinues the study within 30 days after the dose of study drug, a Safety Follow-up Visit will be conducted on 30 days after the dose of study drug. If the premature discontinuation from study occurs within 7 days prior to the timepoint of 30 days after the dose of study drug, the Safety Follow-up Visit could be combined with the EOS Visit as appropriate. A visit window of ± 3 days will be allowed for Safety Follow-up Visit.

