2.2. Study Endpoints

2.2.1. Primary Endpoint

- Incidence and severity of treatment-emergent adverse events (TEAEs) and treatment-emergent serious adverse events (SAEs)

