9.6. Timing, Frequency, and Method of Capturing Adverse Events and Serious Adverse Events

9.6.1. Adverse Event Reporting Period

After informed consent has been signed but prior to the administration of the study drug, only SAEs should be reported.

After initiation of the study drug, all AEs and SAEs, regardless of relationship to study drug, will be reported until 30 days after the dose of study drug or EOS Visit, whichever is later. After the period, the investigator should report any SAEs that are considered to be related to the study drug.

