6.5.2. Adverse Events

The AE verbatim descriptions (investigator terms from the eCRF) will be classified into standardized medical terminology using MedDRA. Adverse events will be coded to the MedDRA lowest level term closest to the verbatim term, along with the linked MedDRA PT and primary SOC.

A TEAE is defined as an AE that had an onset date or a worsening in severity from baseline on or after the administration of study drug and up to 30 days after the dose of study drug. Summary tables will generally focus on those AEs that were treatment-emergent. All AEs, treatment-emergent or otherwise, will be presented in subject data listings.

If any of the following TEAEs occurs, the administration of the study drug and the enrollment of new subjects will pause for the dose level:

- One or more ≥ Grade 4 TEAEs or treatment-emergent SAEs related to study drug as assessed by the investigator in any subject or
- Grade 3 TEAEs related to study drug as assessed by the investigator in 2 or more subjects at the same dose level.

An AE overview table, including the number of subjects with TEAEs, TEAEs with grade 3, TEAEs with grade 4 or higher, treatment-emergent SAEs, TEAEs that led to death, TEAEs that led to treatment discontinuation, TEAEs that led to treatment modification for study drug, and treatment-related TEAEs, will be provided by dose level. Treatment-related AEs include those events considered by the investigator to be related to study drug or with a missing assessment of the causal relationship.

The incidence of TEAEs will be reported as the number (percentage) of subjects with TEAEs by SOC, PT and the worst grade. A subject will be counted only once by the highest severity grade according to NCI-CTCAE version 5.0 within a SOC and PT, even if the subject experienced more than one TEAE within a specific SOC and PT. The number (percentage) of subjects with treatment-emergent SAEs will be summarized by SOC and PT.

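### For subjects who leave within 30 days, the last scheduled safety contact can fall 27 days after the dose, before the 30-day TEAE window of the primary endpoint closes, with none scheduled later

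*Protocol*

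**What the plan says.** Times below are days after the dose unless written as a study Day. Dosing is on Day 1, so study Day 29 is 28 days after the dose.

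- **TEAE window.** The primary endpoint is the incidence and severity of TEAEs and treatment-emergent SAEs (Protocol 2.2.1). SAP 6.5.2 counts events with onset or worsening "on or after the administration of study drug and up to 30 days after the dose of study drug". Protocol 10.3.2 uses the same window.
- **Safety Follow-up Visit.** For a subject who leaves within 30 days, "a Safety Follow-up Visit will be conducted on 30 days after the dose of study drug" (Protocol 7.6.3). The same section adds: "A visit window of ± 3 days will be allowed for Safety Follow-up Visit". Appendix 1, footnote c, repeats both.
- **Combination.** If leaving "occurs within 7 days prior to the timepoint of 30 days after the dose of study drug", then "the Safety Follow-up Visit could be combined with the EOS Visit as appropriate".
- **EOS Visit after early leaving.** Protocol 7.6.2 describes a visit "which is required to be conducted within 7 days after the premature study discontinuation". That sets an upper limit but no lower one. The telephone contact in 7.6.2 is for subjects who refuse or cannot attend the EOS Visit.
- **Reporting period.** Under Protocol 9.6.1, all AEs "will be reported until 30 days after the dose of study drug or EOS Visit, whichever is later". After that, related SAEs are still reported.

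**The concern.** The Safety Follow-up Visit makes it possible to question a subject who has left about the whole 30-day window. A visit held before 30 days cannot do that for the days still to come, and the protocol schedules no contact afterwards for a subject who attended. Subjects who stay in the study do not have this gap. Their Day 43 visit comes after the window has closed, and the standard questions in Protocol 9.6.3 ask about medical problems since the last visit.

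The analysis does not make up for it. Every dosed subject stays in the Safety Analysis Set (SAP 6.1), incidence is a number and percentage of subjects (SAP 6.5.2), and missing data are not imputed unless the SAP says otherwise (SAP 6.2.3). An event in the tail that nobody asks about, and that the subject does not volunteer, is counted as no event.

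The protocol also creates leavers close to this point. Subjects are swabbed at Day 29, and a positive or suspected result means discontinuation from the study (Protocol 8.2.8).

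**Working it through.** The plan gives no figure to reproduce. The check is calendar arithmetic on its own windows.

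**Inputs**
- TEAE window closes at 30 days (Protocol 10.3.2; SAP 6.5.2).
- Safety Follow-up Visit window: 30 − 3 = 27 to 30 + 3 = 33 days (Protocol 7.6.3).
- Combination allowed if the leaving day D is from 30 − 7 = 23 to 30 (Protocol 7.6.3).
- EOS window after leaving on day D: D to D + 7 (Protocol 7.6.2).

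**Formula.** Longest tail without scheduled contact = max(0, 30 − earliest permitted visit day).

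**Separate Safety Follow-up Visit.** The earliest day is 27, so the tail is at most 30 − 27 = 3 days, or 3/30 = 10% of the window.

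**Combined visit.** There are two readings. Under A, only the EOS window binds. Under B, the ± 3-day window binds as well, so the visit must fall in both.

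| Leaving day D | A: permitted days | A: longest tail | B: permitted days | B: longest tail | Days at 30 or later within both windows |
|---|---|---|---|---|---|
| 23 | 23–30 | 7 | 27–30 | 3 | 30 |
| 24 | 24–31 | 6 | 27–31 | 3 | 30–31 |
| 25 | 25–32 | 5 | 27–32 | 3 | 30–32 |
| 26 | 26–33 | 4 | 27–33 | 3 | 30–33 |
| 27 | 27–34 | 3 | 27–33 | 3 | 30–33 |
| 28 | 28–35 | 2 | 28–33 | 2 | 30–33 |
| 29 | 29–36 | 1 | 29–33 | 1 | 30–33 |
| 30 | 30–37 | 0 | 30–33 | 0 | 30–33 |

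The longest tail is 3 days under B and 7 days under A (7/30 = 23%). The last column shows that a combined visit at 30 days or later already fits both existing windows for every D from 23 to 30.

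**Subjects who stay.** Day 43 is 1008 h / 24 = 42 days, ± 2, so 40 to 44 days after the dose (Protocol 8.4; Appendix 3). That is after the window closes, so their tail is 0.

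**Day 29 swab.** The visit is 672 h / 24 = 28 days, ± 1. If it is held on its nominal day and the result takes 1 to 2 days (my assumption; the documents give no turnaround), discontinuation falls at 29 to 30 days, inside the combination period. A result on the day of the visit would put it at 28 days. An EOS Visit on the day of leaving then leaves a tail of 0 to 2 days on either reading.

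**The case against.** The strongest reply is that little is lost.

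- **A reader might infer that a visit at 23 days is plainly permitted.** The documents do not establish that. In 7.6.3 the ± 3-day sentence comes after the combination sentence and makes no exception for a combined visit. Footnote c attaches the window to the visit itself. The 7-day combination rule also matches the 7-day EOS limit, so a subject who leaves at 23 days can still be seen at 30. This stands: 23 days is one reading, while 27 days needs no interpretation.
- **A reader might infer that early leavers as a group have no contact after the window closes.** That is too strong. The same windows allow visits at 30 to 33 days, and subjects who leave before 23 days have a separate visit nominally at 30.
- **A reader might infer that the tail is wholly unobserved.** It is not. Protocol 9.6.1 keeps reporting open to at least 30 days, 9.3.4 requires known events to be followed, 9.7.2 has subjects told to report delayed reactions, and 8.5 allows unscheduled visits at the subject's request. These routes depend on the subject coming forward or on an event already known. They do not replace a scheduled question about new events.
- **A reader might infer that incidence at a dose level shifts by 1/6 = 16.7 points.** That needs an active subject with no earlier TEAE who leaves early, is last seen before 30 days, and has a first event in the tail that goes unreported. Someone who left for tolerability reasons already has a TEAE, so only severity or an SOC/PT row could change. If the leaver is replaced, the denominator is 7 and the shift is 1/7 = 14.3 points.

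The study is also descriptive, with no hypothesis test, and a symmetric visit window is an ordinary scheduling choice. Those points lower the weight of the gap but do not remove it.

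**Conclusion.** The point holds in a limited form. The ± 3-day window allows the last scheduled contact of an early leaver to fall 27 days after the dose, and the text does not say whether that window governs a visit combined with EOS. Active elicitation of TEAEs can therefore stop up to 3 days before the primary-endpoint window closes, or up to 7 days if the combined visit is bound only by the EOS limit. Only subjects who leave within 30 days are concerned.

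The documents give no dropout rate, so the number affected cannot be computed; total enrolment of at most 30 is the only bound. The effect on subject-level incidence is confined to a first, unreported TEAE in the tail in a subject with none before. This is a cheap improvement of low severity, not a threat to the primary endpoint.

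**What to change.** In Protocol 7.6.3 and Appendix 1, footnote c:

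1. Change the Safety Follow-up Visit window from ± 3 days to 0/+3 days.
2. State that this window also governs a visit combined with EOS, so that the two are combined only when the EOS Visit falls 30 days after the dose or later.
3. Where the last visit was held before 30 days, add one AE telephone call at 30 days or later, for subjects who have not withdrawn consent to contact.

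The cost is slightly less scheduling flexibility, or one telephone call for a few subjects. A subject who leaves at 23 days could combine the visits only at 30 days. No extra subjects or samples are needed. No schedule change secures contact with a subject who withdraws consent, since Protocol 9.3.4 ends follow-up there.

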7.6.4. Lost to Follow-up

If attempts to contact a subject by telephone are unsuccessful, additional attempts should be made during the study to complete study-related assessments and record outstanding data. It may be possible to obtain the information from other contacts, such as referring physicians, or primary care providers.

Attempts to contact should be documented in the subject's source documents. If a subject cannot be contacted despite all attempts, the subject will be considered lost to follow-up.

7.7. Discontinuation From Study Treatment or From the Study

7.7.1. Subject Discontinuation From the Study Treatment

Eligible subjects will receive a single dose of study drug and they have the right to discontinue the study drug at any time for any reason during the study treatment. In addition, the investigator

has the right to discontinue a subject from the study drug at any time during the study treatment. Subjects who discontinue the study treatment should follow the procedures and the assessments specified in EOS Visit (Section 7.6.2). The subject who could not complete the infusion should be replaced.

The primary reason for discontinuation from the study treatment should be documented on the appropriate eCRF. Subjects may discontinue from the study treatment for reasons that include, but are not limited to, the following:

- Withdraw of consent
- The investigator or sponsor determines it is in the best interest of the subject
- Significant or persistent AE(s) as described in Section 9.7.

7.7.2. Subject Discontinuation From the Study

Subjects may discontinue from the study for reasons that include, but are not limited to, the following:

- Subject withdrawal of consent
- Study termination by sponsor
- Lost to follow-up
- Completion of all study assessments
- Positive for COVID-19

Subjects may voluntarily withdraw consent from the study at any time. The subject who discontinues from the study before Day 29 may be replaced.

7.8. End of Study

The end of study is defined as the timepoint when the final data for a clinical study were collected, which is after the last subject has made the final visit to the study center.

Alternatively, the end of study is when the sponsor decides to terminate the study. The sponsor has the right to terminate this study at any time. Reasons for terminating the study early include, but are not limited to, the following:

- The incidence or severity of AEs in this or other studies on BGB-DXP593 indicates a potential health hazard to subjects
- Overall subject enrollment is unsatisfactory

The sponsor will notify the investigator if a decision is made to terminate the study. Should this be necessary, prematurely discontinued subjects must be seen for an EOS Visit as described in Section 7.6.2.

The investigators may be informed of additional procedures to be followed to ensure that adequate consideration is given to the protection of the subject's interests. The investigator will be responsible for informing IRBs/IECs of the early termination of the study.

8. STUDY ASSESSMENTS

A table of scheduled study assessments is provided in [Appendix 1](#). Subjects will be closely monitored for safety and tolerability throughout the study. All assessments will be performed on the day of the specified visit and documented in the medical record for each subject.

Where applicable, the single dose of study drug will be administered only if the clinical assessment and laboratory test values have been reviewed and found to be acceptable per protocol guidelines.

8.1. Screening Assessments

Screening evaluations will be performed within 28 days before receiving the study drug. The screening period begins on the first day that a screening assessment is conducted. The investigator will assess subject eligibility according to the latest screening assessment results.

8.1.1. Demographic Data, Medical History, and Prior Medications

Demographic data will include age or year of birth, gender, and race/ethnicity.

Medical history includes any history of clinically significant disease, surgery history, reproductive status (ie, no childbearing potential or childbearing potential), and smoking history.

Prior medications include all medications (eg, prescription drugs, over-the-counter drugs, herbal medications) used by the subject within 28 days prior to the single study dose.

8.2. Safety Assessments

8.2.1. Vital Signs

Vital signs will include measurements of body temperature (°C), pulse rate, respiratory rate, and blood pressure (systolic and diastolic). Pulse rate and blood pressure will be measured while the subject is in a supine position after resting for 10 minutes.

Height and weight will be measured at screening and weight will be measured again before the single dose of study drug on Day 1. The data of height and weight will be recorded in the eCRF.

8.2.2. Physical Examinations

During the Screening Visit, a complete physical examination will be conducted, including evaluations of 1) head, eyes, ears, nose, and throat, 2) cardiovascular, 3) dermatological, 4) musculoskeletal, 5) respiratory, 6) gastrointestinal, and 7) neurological systems. Any abnormality identified during screening will be graded according to NCI-CTCAE version 5.0 and recorded in the eCRF with appropriate disease/condition terms.

At subsequent visits (and as clinically indicated), limited, symptom-directed physical examinations will be performed. New or worsened clinically significant abnormalities are to be recorded as AEs in the eCRF. Refer to [Section 9.3](#) regarding AE definitions and reporting and follow-up requirements.

8.2.3. Laboratory Safety Tests

Samples for protocol-specified clinical chemistry, hematology, urinalysis, and coagulation profiles will be evaluated by a local laboratory.

Pregnancy test will be performed for female subjects of childbearing potential during the study. Samples for pregnancy testing will also be assessed locally. The serum pregnancy test will be performed at the Screening Visit, and the next serum pregnancy test will be conducted after the admission on Day -1 and before the dose of study drug on Day 1. Female subjects of childbearing potential with negative results will be eligible to receive the study drug. Afterwards, urine pregnancy test will be performed. A serum pregnancy test must be performed if the urine pregnancy test is positive or equivocal.

See [Appendix 4](#) for the list of clinical laboratory tests to be performed and [Appendix 1](#) for the timing and frequency. Additional tests may be performed at any time during the study as deemed necessary by the investigator or as required by local regulations. If required by local regulations, clinical laboratory evaluations performed by a local (instead of a central) laboratory are acceptable.

A detailed description of the procedures for sample collection, handling, storage, and shipment of the laboratory samples and all materials such as test tubes and labels are provided in the Laboratory Manual.

